5.2. Timing of Analyses

The adaptive study design is based on periodic analysis of symptoms and infection status to determine whether dose escalation criteria have been met. These analyses are blinded, assessing the attack rate across all participants at a given dose level, regardless of receipt of active challenge virus or sham inoculum.

The CSR will be completed when all primary and secondary safety, clinical, and immunological endpoint data are available. Any available data from the exploratory endpoints may also be included. Additional exploratory endpoint data would be included in an addendum to the CSR or standalone analysis report(s) to be incorporated into manuscripts.

A topline report to facilitate timely reporting of primary and secondary objective analysis results will be generated prior to the compilation of the CSR. This will consist of a select portion of tables, which are indicated in [Appendix 1](#) with asterisks alongside titles. These results will be final and will be included in the CSR as well. A portion of these analyses will be presented at the CIVICs network’s 2023 annual meeting, prior to publishing the results in the National Library of Medicine (clinicaltrials.gov).

5.3. Analysis Populations

Analyses will be conducted within one of the following populations, or in subsets of these populations, such as infected participants, or those receiving what is determined to be the optimal dose.

5.3.1. Safety (SA) Population

The Safety population will include all participants who received study influenza challenge or sham inoculum.

5.3.2. Intent-to-Treat (ITT) Population

The Intent-to-Treat population will consist of all enrolled participants.

5.3.3. Per Protocol (PP) Population

The Per-Protocol population will include participants in the ITT population with the following exclusions of data:

- All data from any participants who withdraw prior to the end of the challenge period
- Data from any visit that occurs substantially out of window
- Data from all visits subsequent to major protocol deviations that could impact the validity of later data, such as:
 - Study ineligibility at enrollment (determined thereafter)
 - Receipt of immunosuppression or any medications that may be associated with impaired responsiveness
 - Receipt of any investigational drug/investigational vaccine/licensed vaccine
 - Receipt of blood or blood products, or blood donation

5.4. Covariates and Subgroups

Exploratory analysis will include an assessment of the association between the following covariates and development of symptomatic influenza illness: age (continuous), sex (male, female), prior receipt of seasonal influenza vaccine(s) or viral challenge (yes/no), and clinical site (DU or UMD).

The protocol does not define any formal subgroup analyses, and the study was not powered to perform subgroup analyses.

5.5. Missing Data and Outliers

All attempts are made to collect all data per protocol, and missing data are expected to be minimal due to the nature of the study, with participants in confinement units for much of the follow-up period. No imputation is planned for missing data.

Any data point that appears to be erroneous or inexplicable based on the observed data distribution and the statistical team's understanding of the analysis variables will be investigated as a possible outlier. If data points are identified as outliers, sensitivity analyses may be performed to examine the impact of including or excluding the outliers. Any substantive differences in these analyses will be reported.

5.6. Interim Analyses and Data Monitoring

No formal interim analysis is planned., but analysis of symptoms and infection status is performed after completion of the confinement period for each dosing cohort to determine whether dose escalation criteria have been met.

A safety monitoring committee (SMC) meets to review safety and disposition data at scheduled time points or ad hoc as needed during this study, as delineated in the SMC charter.

5.7. Multicenter Studies

For most analyses, data will be pooled across both clinical sites. While the two sites use standardized procedures and rely on central laboratories for the assessment of immunogenicity and clinical endpoints, some exploratory analysis will be conducted within site-specific subgroups.

5.8. Multiple Comparisons/Multiplicity

Analysis will be primarily descriptive, but hypothesis testing results will be reported for regression models and some other selected comparisons of interest. No adjustments for multiplicity are planned, but the number of comparisons made will be factored into the interpretation of results, as appropriate.

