#### 9.5.1 General Approach

For descriptive analyses, continuous variables will be summarized by the non-missing sample size, mean, standard deviation, and the minimum, median, and maximum. Categorical variables will be summarized by frequencies and percentages of observed levels, based on the non-missing sample size. Titers will be summarized with geometric means, first across replicates to compute one value for each individual sample and then applied again across subjects within the same group.

Generally, summaries will be presented by challenge dose group, with sham placebo subjects pooled across all challenge cohorts into one group. For safety endpoints, summaries will include a column for all subjects receiving active challenge virus as well. Other groupings used for some analyses may include symptomatic/asymptomatic, shedding virus yes/no (i.e., RT-PCR+/RT-PCR-), and symptomatic influenza+/symptomatic influenza- or MMID+/MMID-.

Data listings will be presented sorted by clinical site or other grouping variable, subject, and then by visit number within subject, where applicable. All tables will be annotated with the total

population size relevant to that table, including any missing observations. The analysis population for each exhibit will be clearly indicated.

While the study was not designed for any formal group comparisons, hypothesis testing will be done for some endpoints and will be considered exploratory. For hypothesis testing related to safety endpoints, two-sided tests at the  $\alpha$ =0.05-level will be made without adjusting for multiple testing. For hypothesis testing of clinical endpoints, initially a global, two-sided test will be used to determine if there are differences between any groups. If the global test is significant at the  $\alpha$ =0.05-level, the Bonferroni-Holm stepdown procedure [9] will be used to control the type-I error across pairwise two-sided tests, but no adjustment will be made across endpoints; a familywise 5% error rate will be used to determine significance. For immunological, genomic, or physiological analyses involving hypothesis testing, more stringent thresholds for significance may be used, depending on the number of hypothesis tests comprising a related set of analyses.

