Viral shedding will be summarized by the number and percentage of subjects in each challenge dose group with positive qualitative and/or quantitative RT-PCR each day from Day 2 through the end of the challenge period (Day 8 or later, in the case of a subject not meeting discharge criteria on Day 8) excluding safety results reported after receipt of antiviral therapy. The probability of viral shedding at any point during the challenge (i.e., incidence) will be estimated along with the associated exact 95% CI, separately by challenge dose group. Peak viral shedding will be calculated for each subject as the maximum shedding from Day 2 through Day 8 or discharge, and total viral shedding will be calculated via the area under the curve (AUC) with study day on the x-axis and shedding on the y-axis. These will be calculated separately for quantitative RT-PCR and quantitative culture. Mean peak and total shedding based on the AUC will be calculated for each group along with 95% CIs, and comparisons will be made as described for continuous variables in Section 9.5.1. A Wilcoxon signed-rank test will be used to compare distributions of these variables between quantitative RT-PCR and quantitative culture across all subjects, to assess if these methods of viral quantification are consistent. Scatterplots will also be presented, along with Spearman rank-order correlation estimates. Duration of viral shedding will be calculated for each subject as the number of days (including non-consecutive) determined by qualitative or quantitative RT-PCR to be positive from Day 2 until discharge; means and 95% CIs will be calculated for each group and comparisons will be made.

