7.1.2. Influenza Symptoms

The maximum severity of influenza symptoms during the challenge period, reported as part of the Modified Jackson Score and used to determine the AR, will be summarized by challenge dose group in [Table 15](#), and separately by infection status (see [Section 3.2.3](#)) in [Table 16](#) and [Figure 7](#) (infected participants) and [Table 17](#) and [Figure 8](#) (uninfected participants). Symptoms reported on Study Day 15 will be presented similarly in [Table 18](#) and [Table 19](#). Symptoms over the challenge period will also be summarized by infection status, independent of challenge dose group, in [Table 20](#), and Day 15 symptoms will be presented in [Table 21](#).

New-onset symptoms (see [Section 3.2.3](#)) among infected participants will be summarized in [Figure 9](#), and the maximum severity of symptoms will be summarized by concurrent infection status in [Table 26](#). Wilcoxon signed rank tests will be used to compare maximum severities among infected participants: pre-infection to during infection, post-infection to during infection, and pre-infection to post-infection, in [Table 27](#). No p-value adjustment is planned for multiple comparisons, but the number of comparisons made will be considered when interpreting the results. Current/concurrent infection status is defined in [Section 3.2.3](#).

The maximum symptom severities reported for each study day during the challenge period and at any point post-challenge will be summarized for currently infected participants, separately by challenge dose group in [Table 22](#) through [Table 25](#). At baseline and Day 1, all participants will be included in these summaries, as a comparison for post-infection symptoms.

Total MJS scores during the challenge period will be presented by study day and challenge group in [Figure 10](#), with RT-PCR+ study days indicated with annotation in the given cell.

MJS symptoms will be presented in detail in [Listing 8](#).

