13. TECHNICAL DETAILS

SAS version 9.4 or above, or R version 4.2 or above, will be used to generate all tables, figures and listings.

**14. SUMMARY OF CHANGES IN THE CONDUCT OF THE STUDY OR
PLANNED ANALYSES**

No substantive changes to the analysis planned in the protocol have been made.

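### The SAP plans no multiplicity adjustment and omits the dose-group tests for which the protocol sets a global test plus Holm at a familywise 5%, and SAP section 14 does not record the change.

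*SAP*

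**What the plan says.** Protocol 9.5.1 sets the rule. The first stage is a screen: "For hypothesis testing of clinical endpoints, initially a global, two-sided test will be used to determine if there are differences between any groups". If that test is significant at 0.05, "the Bonferroni-Holm stepdown procedure [9] will be used to control the type-I error across pairwise two-sided tests", and "a familywise 5% error rate will be used to determine significance". The same paragraph calls the testing exploratory. The section ends by requiring that any other approach be stated and justified in the SAP or the clinical study report.

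Protocol 9.5.2 then uses the rule. For shedding, "Mean peak and total shedding based on the AUC will be calculated for each group along with 95% CIs, and comparisons will be made" by the methods of 9.5.1. It also plans group comparisons for duration of shedding and for the total symptom scores.

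SAP 5.8 reads: "No adjustments for multiplicity are planned, but the number of comparisons made will be factored into the interpretation of results". SAP 7.1.2, which sits under the primary clinical analysis, covers the Wilcoxon signed-rank tests of Table 27 (before, during and after infection, within infected participants) and says: "No p-value adjustment is planned for multiple comparisons". The shells of Tables 36 and 43 give means and confidence intervals by dose group but no p-values. SAP section 14 reads: "No substantive changes to the analysis planned in the protocol have been made".

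**The concern.** The two documents give different answers to a simple question: when is a difference in a clinical endpoint called significant? The protocol has a decision rule. The SAP has raw p-values and a promise to bear their number in mind, which is not a rule.

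There are two separate departures. The dose-group comparisons that the protocol planned under its rule are absent from the tables that would hold them. And the paired comparisons that the SAP added are reported without a global test or an adjustment. Section 14 tells the reader of the study report that neither happened. A symptom change could then be described as significant when it would fail the protocol's own criterion, with nothing in the report to show that the criterion had been dropped.

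**Working it through.** **Inputs**
- Protocol 9.5.1: global two-sided test at 0.05, then Holm, familywise 5% within an endpoint.
- SAP 7.1.2 and the Table 27 shell: three paired tests per row; 15 rows (any symptom plus 14 individual signs or symptoms), so 15 × 3 = 45 p-values; no global test and no adjusted column.
- Level per test: 0.05, assumed. The SAP gives none; its section 12 covers only how p-values are printed.

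**1. The protocol's figure.** For three tests the Holm thresholds, from smallest p-value to largest, are 0.05/3 = 0.0167, 0.05/2 = 0.025 and 0.05. The bound is 3 × 0.0167 = 0.05, the stated 5%. In a normal-theory simulation of three exchangeable phases with no true difference (400,000 runs), Holm alone gave 4.4% and the global test plus Holm gave 4.2%.

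**2. The same three tests unadjusted at 0.05.**
- If independent: 1 − 0.95³ = 0.143.
- All pairwise contrasts of three exchangeable phases (correlation 0.5), by the studentized range: 1 − F(1.96 × √2; 3 means, large df) = 0.122. The simulation gave 0.122.

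**3. On the 0 to 3 severity scale.** Chance of at least one p ≤ 0.05 per symptom with signed-rank tests (normal approximation, 3,000 runs each, assumed severity distributions, phases drawn independently from the same distribution):

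| Share scoring 0 / 1 / 2 / 3 (%) | n=10 | n=20 | n=40 | n=70 |
|---|---|---|---|---|
| 50 / 30 / 15 / 5 | 0.099 | 0.115 | 0.119 | 0.120 |
| 80 / 12 / 6 / 2 | 0.047 | 0.106 | 0.121 | 0.115 |
| 95 / 3 / 1.5 / 0.5 | 0.0003 | 0.009 | 0.052 | 0.104 |

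A separate ordinal simulation with 15, 20 and 30 infected participants gave 0.103, 0.120 and 0.127 unadjusted. With a Friedman test first and then Holm, it gave 0.020, 0.026 and 0.028.

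**4. Where the two rules disagree.** Take illustrative p-values for one symptom.
- 0.03, 0.20, 0.60: one is below 0.05 unadjusted. Under Holm the smallest must be at most 0.0167, so none is significant (adjusted 3 × 0.03 = 0.09).
- 0.004, 0.02, 0.04: all three pass Holm (0.004 ≤ 0.0167, 0.02 ≤ 0.025, 0.04 ≤ 0.05).

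So the rules disagree on whether a symptom shows any difference when its smallest p-value lies between 0.017 and 0.05. A larger p-value in that range can still be significant once the earlier steps are passed. In the normal-theory simulation, 4% of p-values in that range (no true difference) to 25% (strong effect during infection) stayed significant.

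**5. The dose-group tests.** No arithmetic applies. Protocol 9.5.2 plans group comparisons of peak and total shedding, duration and symptom scores; Tables 36 and 43 contain none.

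**The case against.** The protocol leaves room. Section 9.3.2 says p-value adjustments may be made depending on the objective, and points to 9.5.1 and the SAP for detail. Section 9.5.1 allows other approaches. The SAP states its choice twice, and the study report could still supply the reason. This stands in part: the sponsor was free to change the rule. But neither SAP 5.8 nor 7.1.2 gives a reason, and section 14 denies any substantive change.

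The rule is worded for differences between groups. Table 27 compares phases within the same infected participants, which the protocol does not list. This also stands. Extending the rule to Table 27 is a reasonable reading of a rule for hypothesis tests of clinical endpoints, not an explicit instruction. It does not help with Tables 36 and 43, whose dose-group comparisons are the use for which the rule was written.

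Missing tests cannot inflate type I error. Correct: the gap in Tables 36 and 43 is an undeclared omission, and the error figures concern Table 27 only.

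Finally, all this testing is exploratory, and the optimal dose is chosen in Protocol 9.5.2 from the estimated attack rate, its confidence interval and the halting criteria, with no test. That limits the consequence. It does not remove the mismatch, because the paragraph that calls the tests exploratory also fixes their significance rule.

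**Conclusion.** The point holds in a limited form and is worth correcting. The SAP drops the protocol's familywise 5% control for clinical endpoints and the dose-group comparisons of shedding and symptom scores, gives no justification, and declares no substantive change. In Table 27, three unadjusted tests at 0.05 give about 10 to 12% error for a common symptom, against at most 5% under the protocol rule. This assumes a 0.05 level per test, no true difference between phases, exchangeable phases and the severity distributions shown.

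A reader might infer more than the documents support:
- **That every p-value between 0.017 and 0.05 changes status.** This is true only of the smallest of the three; Holm is more lenient at later steps.
- **That the SAP itself calls p = 0.03 significant.** It sets no level, so such a result is only nominally significant at the protocol's 0.05.
- **That every symptom runs at 12%.** For a rare symptom the rate was below 1% at n = 10 and n = 20, and about 5% at n = 40.
- **That error should be controlled over all 45 p-values.** Protocol 9.5.1 says Holm "will be used to control the type-I error across pairwise two-sided tests, but no adjustment will be made across endpoints", so an error rate over the whole table is not a breach of either document.
- **That the choice of dose is at risk.** It is not.

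**What to change.** - **Tables 36 and 43:** add the protocol's global two-sided test across challenge dose groups and, where it is significant at 0.05, Holm-adjusted pairwise p-values. State whether sham belongs to the family, since three dose groups give 3 pairs and four groups give 4 × 3 / 2 = 6.
- **Table 27, SAP 5.8 and 7.1.2:** for each symptom run one global paired test over the three phases (Friedman is one option; neither document names a test). If it is significant at 0.05, show Holm-adjusted p-values beside the raw ones and judge significance on the adjusted values. State the level.
- **SAP section 14:** if the sponsor drops any of these tests or keeps raw p-values, label the p-values descriptive, and list and justify each departure there in place of the statement of no substantive change.

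The cost is a few lines of text and minor programming, with no new data. Some nominal p-values will look less favourable, and Friedman plus Holm is conservative on this scale (2 to 3% in the simulation above). The descriptive route resolves the discrepancy equally well if the reason is recorded.

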6. STUDY PARTICIPANTS

6.1. Demographic and Other Baseline Characteristics

Sex, race, ethnicity, age, and BMI will be summarized by site in [Table 9](#) and [Table 10](#) and by challenge dose group [Table 11](#) and [Table 12](#). Age will be summarized as both a categorical and continuous variable. Baseline characteristics will be detailed per participant in [Listing 6](#).

6.2. Disposition of Participants

Screening failures will be summarized in [Table 8](#). A summary of participant disposition will be presented in [Table 6](#), including the total number of participants screened, enrolled, challenged, terminated early, and having completed the last follow-up visit.

The number and percentage of enrolled participants excluded from each analysis population are presented in [Table 7](#). A listing of participants excluded from each analysis population will be presented in [Listing 5](#).

A flowchart showing the disposition of study participants, adapted from the CONSORT Statement, will be included and will present the number of participants screened, challenged, lost to follow up, and analyzed ([Figure 6](#)).

A listing of participants who discharged early or terminated from study follow-up and the reason will be included in [Listing 2](#), where details about missed follow-up visits related to the Coronavirus Disease 2019 (COVID-19) pandemic will be included.

6.3. Prior and Concurrent Medical Conditions

All current illnesses and past or pre-existing medical conditions will be coded using Medical Dictionary for Regulatory Activities (MedDRA®) version 25.1 or higher.

Summaries of participants' prior and concurrent medical conditions will be presented by challenge dose group and MedDRA system organ class in [Table 13](#).

Individual participant listings will be presented for all reported medical history including prior and concurrent medical conditions in [Listing 7](#).

6.4. Prior and Concomitant Medications

Prior (within 90 days of enrollment) and concomitant medications will be coded to the Anatomical Therapeutic Classification (ATC) using the WHO Drug Dictionary. The use of concomitant medications during the study will be summarized by ATC1 and ATC2 code, as well as challenge dose group, for the Safety population in [Table 79](#).

A listing of concomitant medications will be presented in [Listing 17](#).

6.5. Measurements of Study Product Compliance

Participants are directly observed at the time of dosing by a member of the clinical research team licensed to administer the study product. The number of participants receiving the challenge virus or sham inoculum will be presented as part of the participant disposition table ([Table 6](#)). The timing of challenge and study assignment will be presented for all challenged participants in [Listing 1](#).

6.6. Protocol Deviations

A summary of participant-specific protocol deviations will be presented by the reason for the deviation and the deviation category for all enrolled participants ([Table 3](#)). All participant-specific protocol deviations and non-participant-specific protocol deviations will be included in [Listing 3](#) and [Listing 4](#), respectively.

7. CLINICAL EVALUATIONS

Analysis of clinical endpoints that do not involve immunoassays will be done in the Safety population. Analyses involving immune responses will be conducted using the ITT population. If at least 10% of analysis data would be excluded by the reasons given in [Section 5.3.3](#), some analyses may be conducted in the PP population as well, as a sensitivity analysis.

7.1. Primary Clinical Analysis

7.1.1. Symptomatic Influenza Attack Rate

The primary objectives of the study include determining the optimal dose of the study challenge virus, for future use as a clinical challenge strain in vaccine efficacy or intervention studies. This evaluation includes an objective assessment of the AR for symptomatic influenza infection (as defined in [Section 3.2.1](#)), with additional primary objectives to further describe the symptoms and the viral detection via RT-PCR (qualitative and quantitative) for each challenge dose group and cross-tabulated by the other related outcomes.

The symptomatic influenza AR will be analyzed by challenge dose group in [Table 14](#), along with component outcomes and a summary of the per-participant maximum cumulative MJS score during the challenge period, and the total MJS score at Day 15.

